Title: Threat Interpretation Bias as Cognitive Marker and Treatment Target in Pediatric Anxiety: R61 Phase

NCT NUMBER: NCT04245501

Revised document date: 02/20/2020

PROJECT SUMMARY AND SPECIFIC AIMS:

Anxiety is the most common mental health problem in youth, affecting one in four children and adolescents. Unfortunately, evidence-based interventions (pharmacotherapy, cognitive-behavioral therapy) are costly, not widely available, and ineffective for a substantial proportion (~50%) of youth. In response, experts have called for novel *treatments that directly target mechanisms underlying youth anxiety* while simultaneously addressing barriers to care (i.e., cost, accessibility). One such promising mechanism is interpretation bias - the inaccurate interpretation of threat from ambiguity. We have previously demonstrated that interpretation bias occurs in over 90% of anxious youth, accounts for 46% of variance in anxiety severity above and beyond demographic and clinical characteristics, and differentiates between anxious and non-anxious youth. These data indicate that *interpretation bias is a ubiquitous phenomenon underlying anxiety expression in children and adolescents* and therefore may be an *ideal intervention target*. Cognitive bias modification for *interpretation bias* (CBM-I) is a computerized intervention that attempts to reduce anxiety symptoms by directly modifying interpretation bias; participants are provided with real-time corrective feedback when they select threat-relevant interpretations of ambiguity. CBM-I has demonstrated preliminary efficacy for reducing anxiety symptoms in adults. Yet extant CBM-I data in youth are sparse, and several critical questions have not been answered: 1) is the targeted mechanism (interpretation bias) modified by CBM-I in youth?; 2) what dose reflects meaningful interpretation bias change?; and 3) is interpretation bias reduction the mechanism underlying anxiety symptom reduction? Consistent with NIMH strategies to “define mechanisms” and “accelerate therapeutics”, we propose to test interpretation bias as a putative intervention target. This proposal includes a two-phased study of *personalized* CBM-I in youth ages 10 to 17 who meet diagnostic criteria for anxiety disorder (generalized, social, separation). In the R61 Phase (N=46), an RCT examines whether CBM-I personalized to youth anxiety symptoms engages the interpretation bias target, compared to a computerized interpretation control condition (ICC). Our Go/No-Go Milestones reflects a significant difference in interpretation bias reduction between groups (CBM-I outperforms ICC). The interpretation target will be measured at multiple time points (4, 8, 12, 16 sessions) to identify the optimal dose for target engagement.

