
Aim 1: Directly engage and modify interpretation bias. *We predict that, compared to ICC, personalized CBM-I will result in significantly greater reduction of interpretation bias on at least two of three measures: objective linguistic interpretation bias via a word-sentence association paradigm^{6,7}, objective visual interpretation bias via an ambiguous faces task¹², subjective questionnaire of threat attributions.¹³*

Aim 2: Determine CBM-I dose for R33 Phase and subsequent trials. *Dosing is a critical issue relevant to target validation. Interpretation bias will be assessed at four CBM-I doses (4, 8, 12, 16 sessions) in order to identify the optimal dose at which bias reduction occurs.*

Aim 3: Ascertain feasibility and acceptability of approach. *We predict that CBM-I will be feasible with youth, and acceptable to youth and parents.*

R61 GO/NO-GO MILESTONES FOR R33 PHASE:

To proceed to the R33 Phase, CBM-I in the R61 Phase must meet the following criteria:

- 1) **target engagement** on at least two of three interpretation bias outcomes (described above) as reflected by a significant medium effect ($d=0.50$) between groups from pre-to-post-intervention.
- 2) be **feasible** in regards to administration (average of 90% training sessions completed) and rated as **acceptable** (average score of 30 out of 50 on self-reported exit interview¹⁴) to youth and parents.

STATISTICAL ANALYSIS PLAN:

Aims 1 and 2. Multilevel modeling (using Mplus 8.4 [Muthén & Muthén, 2022] software) will examine changes in interpretation bias assessed via both objective (word-sentence association paradigm [WSAP], ambiguous face task [FACES]) and subjective (CATS) measures. Given that some enrolled participants may be siblings, we will adjust all analyses for within-family correlations. In order to estimate the importance of modeling the family-level variance separately from the person-level variance, we will first estimate the Intraclass Correlation Coefficient (ICC) for the three-level model of each target outcome as the proportion of the between-person variability that is between families = (Level 3 variance)/(Level 3 + Level 2 variance). Three-level models will be utilized for outcomes where ICC is high, and two-level model (i.e., observations at level 1 clustered within individuals at level 2) for low ICC that adjust standard errors chi-square statistics for the family-level clustering, using TYPE=TWOLEVEL COMPLEX analysis in Mplus (Muthén & Satorra, 1995).

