Aim 3. In regards to treatment completion and feasibility, we will examine the percentage of youth who completed all 16 trainings, and the proportion of trainings completed by youth who did not complete all 16 trainings. In regard to acceptability, youth and caregivers will complete the Participant/Parent Acceptability Questionnaire and Exit Interview (PAQ). The PAQ assesses how much computer tasks (i.e., bias assessments and trainings) made participants feel tired or bored, whether the computer trainings helped the youth feel less worried, nervous, scared or stressed, whether it was difficult to remember to complete at-home trainings, barriers to participation (i.e., travel, time off work/school, etc.), an overall/global rating for their experience with the study, and whether they would recommend the study to a friend. PAQ total scores range from 0 to 50, with higher scores indicating higher acceptability of the computerized intervention and related training session procedures. Scores of 30-39 indicate at least moderate acceptability, with scores of 40-50 indicating high acceptability. Given that CBM-I and ICC may be associated with differential acceptability, we will also compare acceptability ratings for youth and caregivers between randomized groups with t-tests.

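### Could CBM-I pass the acceptability milestone only because youth who stopped early gave no exit-interview score?

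*Combined protocol and SAP*

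**What the plan says.** Criterion 2 under R61 Go/No-Go Milestones sets two requirements. The lead-in makes clear which arm is judged: "CBM-I in the R61 Phase must meet the following criteria". Feasibility is an "average of 90% training sessions completed". Acceptability, as rated by youth and parents, is an "average score of 30 out of 50 on self-reported exit interview".

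The Statistical Analysis Plan, Aim 3, describes how both are assessed. For completion it reports the percentage of youth who finish every training and, separately, "the proportion of trainings completed by youth who did not complete all 16 trainings". For acceptability it says that "youth and caregivers will complete the Participant/Parent Acceptability Questionnaire and Exit Interview (PAQ". It then gives the content, the 0 to 50 range and the score bands of the questionnaire, and plans t-tests of the ratings between the randomised arms. It does not say when the PAQ is given, whether early leavers are asked for it, or what happens to a missing score.

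**The concern.** The acceptability average decides, in part, whether the programme continues. Aim 3 foresees youth who stop before session 16 and describes their sessions, yet it has no matching sentence about their PAQ scores. The t-test, the only named PAQ analysis, simply omits anyone without a score.

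The omission could also have a direction. Among other things, the PAQ covers tiredness, boredom and "whether it was difficult to remember to complete at-home trainings, barriers to participation (i.e., travel, time off work/school, etc". These are plausible reasons to stop. If those who stopped for such reasons gave no PAQ, the available scores would overstate acceptability, and CBM-I could clear 30 on the ratings of those who stayed. The neighbouring 90% criterion does not rule this out, because it can be met with several early stoppers.

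**Working it through.** The plan derives no figure for acceptability, so there is nothing to reproduce. The check asks how many scores could be missing while the 90% criterion is still met, and how far that could move the mean.

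**Inputs from the documents.** N = 46 (Project Summary and Specific Aims); 16 sessions; 90% average completion and a mean of 30 (milestone criterion 2); PAQ range 0 to 50 (Aim 3).

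**Assumptions.** Allocation is 1:1, so n = 46/2 = 23 in CBM-I (the ratio is not stated). Completion is averaged over all youth randomised to CBM-I (not stated). All other youth finish every session. No stopper gives a PAQ. Stoppers would have averaged m = 20 or 25.

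**Step 1: stoppers allowed.** Total sessions are 23 × 16 = 368, and 10% of that is 36.8, so at most 36 may be missed. A youth who stops after s sessions misses 16 − s, so the largest number of stoppers is k = 36/(16 − s), rounded down.

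**Step 2: observed mean needed.** For a mean of 30 over all 23, those with scores must average 30 + k(30 − m)/(23 − k). An observed mean from 30 up to that value passes although the all-randomised mean is below 30.

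| Stop after session | Largest k | Completion | Upper limit, m = 20 | Upper limit, m = 25 |
|---|---|---|---|---|
| 0 | 2 | 336/368 = 91.3% | 30 + 20/21 = 30.95 | 30 + 10/21 = 30.48 |
| 4 | 3 | 332/368 = 90.2% | 30 + 30/20 = 31.50 | 30 + 15/20 = 30.75 |
| 8 | 4 | 336/368 = 91.3% | 30 + 40/19 = 32.11 | 30 + 20/19 = 31.05 |
| 12 | 9 | 332/368 = 90.2% | 30 + 90/14 = 36.43 | 30 + 45/14 = 33.21 |

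Example: 19 scores averaging 31 and 4 missing at 20 give (19 × 31 + 4 × 20)/23 = 669/23 = 29.1, a pass that all 23 scores would not have supported.

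**Step 3: how bad leavers' scores must be.** With k missing and an observed mean of M, the result reverses only if leavers average below (30 × 23 − M(23 − k))/k.
- k = 4, M = 32: (690 − 608)/4 = 20.5.
- k = 4, M = 34: (690 − 646)/4 = 11.
- k = 2, M = 32: (690 − 672)/2 = 9.
- k = 2, M = 34: (690 − 714)/2 = −12, which is impossible on a scale that starts at 0.

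**Step 4: other allocations.** With 15 in CBM-I, 24 of 240 sessions may be missed, so 3 may stop after session 8, and the limit at m = 20 is 30 + 30/12 = 32.5. With 31, 49 of 496 may be missed, so 6 may stop, and the limit is 30 + 60/25 = 32.4. The split matters little.

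**Step 5: the plan as written.** If leavers are interviewed when they exit, k = 0 and the distortion is nil.

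**The case for a change.** The strongest case for a change is that a hard threshold needs its rules fixed before the data are seen, above all for results near the threshold. Calling the PAQ an exit interview does not guarantee that leavers are asked, and asking does not guarantee an answer. A few sentences would settle the denominator and the handling of missing scores at almost no cost. If completion were averaged over fewer than all randomised youth, the caps in Step 1 would loosen.

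Part of this stands. The documents contain no rule for a missing PAQ score, the arithmetic is correct, and both halves of criterion 2 can be met while the all-randomised mean is below 30.

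The rest is weaker. The sentence on the PAQ carries no restriction to completers, and it follows directly on one that recognises non-completers. An exit interview can be held whenever someone exits. That leavers would score lower is plausible but unsupported: the documents give no reasons for stopping, and the PAQ also asks about perceived benefit, an overall rating and recommending the study. The case of 9 missing means 9/23 = 39% of the arm stopping after three quarters of the training with no PAQ from any of them. That is an extreme, and youth who completed 12 sessions are not an obvious group to presume dissatisfied. Finally, a prespecified missing-score rule would need an assumed score for leavers, and the documents offer no basis for choosing one.

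**Conclusion.** No change is needed. The plan leaves a detail unwritten; it does not state a faulty rule. Read plainly, the PAQ is sought from all youth and caregivers, and the CBM-I average over them is what the milestone calls for. An analyst reporting that average would give the number of scores behind it. Aim 3 already puts completion, including that of non-completers, beside it, so material dropout would be visible to whoever makes the Go/No-Go decision.

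A wrong decision would need several conditions together: several stoppers, no PAQ from them, clearly lower scores, an observed mean just above 30, and success on every other milestone, including target engagement on two of the three bias measures. Under the assumptions above (23 in CBM-I, leavers at 20), the vulnerable range is 30 to about 31.0 with 2 missing and 30 to 32.1 with 4 missing, on a 50-point scale. With an observed mean of 34 and 4 missing, leavers would have to average below 11. The same arithmetic applies to the caregiver mean. The conclusion would differ if the plan limited the PAQ to completers; nothing in the documents does so.
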